Two pilot studies^{61,62} found that combining SDT-based MI interventions with wearable tracker use significantly improved self-reported PA, body weight, and HDL cholesterol in African American men⁶¹ and increased the likelihood of meeting daily step goals in adolescent-parent dyads.⁶² These results present an encouraging possibility for improving PA in sedentary adults: WFTs and SDT based MI. Given the popularity of wearable fitness trackers and the effectiveness of SDT based MI in increasing PA motivation and behavior, the combination of the two shows promise to improve the overall health of adults. Therefore, the purpose of this study is to assess the impact of a self-determination theory motivational interviewing intervention in combination with wearable fitness tracker use on motivation for PA and PA behavior.

Methods

Participant Recruitment and Health Screening

Participants aged 18 and over will be recruited through a variety of means including flyers on the Colorado State University campus, flyers in local fitness centers, physician referrals, social media, and mass emails. In order to detect difference between groups with 95% confidence in repeated measures analyses, we will seek to recruit 40 total participants in order to allow for attrition. We aim to have 32 participants complete the study. To be included in this

study, participants must be over the age of 18 and must not meet physical activity guidelines of at least 150 minutes of moderate physical activity per week. They must own an Android or iPhone smartphone device and be willing to download a mobile application onto that device for use during the intervention. They also must be willing to potentially wear a WFT and/or attend bi-weekly remote MI. Participants must not have a history of heart disease or diabetes, and must not have limiting conditions like concurrent cancer treatment, peripheral artery disease, orthopedic injury, or pain limiting arthritis. They must also not seek to participate in other structured PA programs for the duration of the study, must not be pregnant or seek to become pregnant, and must not have been diagnosed with alcohol or substance abuse during the previous twelve months.

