After having established the eligibility of a potential participant via a screening form, participants will be consented and will complete baseline assessments. This session will involve the administration of all self-reported measures, as well as instruction on accelerometer use. Participants will wear the accelerometer for the subsequent 7 days to provide baseline data on their baseline level of PA. Researchers will collect the ActiGraphs after the 7-day period.

Participants who complete the baseline PA assessment will be invited to a remote session to receive general physical activity guidelines education and will take approximately 1 hour. Prior to this meeting, participants will have been randomly assigned to one of the four study groups (i.e., WFT, MI, WFT+MI, or PA Education Control) using a randomized number generator. To control for age and sex, participants will be age- and sex-matched in each group. During this remote meeting, participants will be informed as to which group they have been randomized into.

Description of Intervention:

The duration of the study will be twelve weeks. The four study conditions are as follows:

WFT: Individuals assigned to this experimental condition will be given a wrist-worn WFT and will be instructed to wear it for the duration of the study. They will also be instructed to download the corresponding mobile application on their smartphones to be used for the duration of the study. They will be trained by a member of our team on how to utilize the WFT and mobile application. The intended WFT tracks daily steps, miles traveled, kcals expended, and daily activity time. This device provides these data to the wearer via a small screen. Participants will be instructed to try and complete at least 150 minutes of PA per week. Researchers will have the capability to track participant daily PA via the WFT mobile application account created for each participant. These individuals will be asked to set biweekly PA goals, which will be emailed to the study coordinator. These participants will also receive general physical activity guidelines education and information on strategies to reach the recommended amount of activity per week during the initial baseline assessment meeting. Participants in this condition will be asked to ONLY wear the WFT provided to them by researchers.

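### Random-number assignment and age- and sex-matching of the four groups are both stated, but no procedure is given that delivers both

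*Combined protocol and SAP*

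**What the plan says.** The assignment text is in the protocol's Methods, under Participant Recruitment and Health Screening. After the baseline week, those who complete it are invited to a remote education session. On assignment the text reads: "Prior to this meeting, participants will have been randomly assigned to one of the four study groups". The tool is given as "using a randomized number generator", and the groups are "i.e., WFT, MI, WFT+MI, or PA Education Control". The next sentence is "To control for age and sex, participants will be age- and sex-matched in each group".

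Nothing links the two sentences. There is no stratification, age band, matching tolerance, block size, minimisation rule, matched set, allocation ratio, list holder or concealment. The paragraph shows no sign of redaction.

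On numbers, the same section says "we will seek to recruit 40 total participants in order to allow for attrition" and "We aim to have 32 participants complete the study".

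The covariate list under Outcome measures includes age but not sex. The Data Analysis section plans an ANCOVA whose covariates are to be chosen from their correlations with the outcomes and with one another. It does not commit to age or sex.

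**The concern.** A statistician given these two sentences could not write the allocation program, so whoever runs the trial has to choose. The two plainest readings each lose something the plan promises.

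- **The draw decides, without restriction.** Assignment is by chance, but age and sex are left to chance too, and so are the arm sizes. With 40 people in four arms, imbalance is likely.
- **The matching decides.** Participants go where someone of their age and sex is needed. Assignment then depends on who places them and what that person knows. Self-reported measures are taken at the baseline session, before the group is announced, and motivation is itself an outcome, so the between-group comparison would lose the protection that randomisation gives.

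In such a small trial, one lopsided arm can colour every comparison that involves it. The planned analysis is not certain to adjust for either matching factor.

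**Working it through.** **Inputs.** From the protocol: 40 recruited, 32 completers, four groups. Assumed because not stated: equal allocation (40/4 = 10 recruited and 32/4 = 8 completers per arm); 50%, 65% or 80% women; age on a standardised normal scale, cut at its mean where two bands are used.

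**The plan's own figures.** 32/40 = 0.80, so the targets imply 20% attrition, and 32/(1 − 0.20) = 40. The 20% is inferred from the targets, so this shows consistency only. The 32 cannot be derived, because no effect size, SD or power is given. The point here does not depend on it.

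**Step 1: arm sizes under an unrestricted draw.**
P(10, 10, 10, 10) = 40!/(10!⁴ × 4⁴⁰) = 0.0039, or 0.4%.
From 400,000 simulated multinomial draws:
- smallest arm 6 or fewer: about 37%; such an arm is below 8 before anyone drops out
- largest and smallest arms differ by 6 or more: about 61%
- mean gap between largest and smallest arm: about 6.5

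**Step 2: sex balance with 10 per arm forced but no stratification.** The counts of women are multivariate hypergeometric. With 20 women among 40, the count differs by 4 or more between some two arms in about 41% of draws. With 26 women (65%) it is about 36%, and with 32 women (80%) about 21%.

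**Step 3: three schemes compared** (20,000 runs each; where three values are shown they are for 50% / 65% / 80% women).

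| Scheme | Proportion of women differs by 30 points or more between some two arms | Mean ages differ by 0.5 SD or more between some two arms |
|---|---|---|
| Unrestricted draw | 58% / 54% / 38% | about 70% |
| 10 per arm, no strata | 67% / 64% / 48% | about 68% |
| Blocks of 4 within sex × two age bands | 0% in all three | about 31% |

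With 10 per arm, 30 points is exactly 3 women, so the first two rows are not finely comparable. The contrast that matters is with the third row. There each arm's assignment probability stayed at about 0.25, participants entered one at a time, and the counts of women never differed by more than 2. Chance assignment and sex balance therefore coexist. Age balance improves but is not guaranteed.

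With block sizes 4 and 8 mixed at random, the same simulation gives counts of women within 2 of each other in about 90% of runs, and differing by 4 or more in under 1%. Mean ages differ by 0.5 SD or more in about 34%.

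**Step 4: predictability.** In a complete set of four, a person who sees earlier assignments guesses correctly with chance 1/4, 1/3, 1/2 and 1 in turn. The mean is (1/4 + 1/3 + 1/2 + 1)/4 = 0.52. In the 40-person simulation, guessing the arm used least so far in the stratum is right about 49% of the time with fixed blocks of 4, because the last block in each stratum is often incomplete. With mixed blocks of 4 and 8 it is about 45%. Minimisation with 80% to the best arm gives about 56–57%; the value depends on the imbalance score and tie rule, and a repeat with another tie rule gave about 59%. Guessing blind gives 25%.

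**The case against.** The strongest reply is that the two sentences do not conflict. A random number generator can drive stratified blocks, minimisation with a random element, or randomisation within matched sets. The text specifies neither an unrestricted draw nor exact individual matching, so the percentages describe schemes that the plan does not state. On this view the paragraph is merely brief. That stands as far as compatibility goes: a reader might infer that the two rules cannot both hold, and step 3 shows that they can.

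Three other inferences go beyond the text:
- **Rolling entry.** The recruitment channels and the individual baseline week make it plausible, but the protocol does not say whether people enter continuously or in cohorts. If in cohorts, matched sets could be formed and randomised without delay.
- **Staff steering.** Nothing says that staff choose arms or match by hand. The text says participants are randomised. Steering is a risk left open by silence on concealment.
- **Assignment before baseline is complete.** Only a latest time is set, but the order of the paragraph points to assignment after the baseline week.

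What the reply does not remove is the gap itself. The plan states a balancing aim and a chance mechanism, and the reader cannot tell which scheme joins them. That choice changes what the trial does, so it is more than a matter of reporting detail.

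**Conclusion.** The allocation method is under-specified in a way that matters. If it is carried out as an unrestricted draw, the stated control for age and sex will often fail: equal arms in 0.4% of draws and, even with equal arms forced, a difference of 4 or more women between some two arms in about 41% (half women assumed; about 21% if 80% are women). If it is carried out by placing people to match, assignment is not by chance. The 0.4% needs only 40 people and four equally likely arms; the balance figures also rest on the assumed sex mix and age scale.

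The documents do not show a contradiction, a loss of randomisation or any steering of participants, and the point should not be cited as if they did. It is a moderate point that should be corrected, with an inexpensive remedy.

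**What to change.** Replace the matching sentence with a single restricted randomisation. One workable version: participants are allocated 1:1:1:1 from a computer-generated list in permuted blocks, sizes 4 and 8 mixed at random, stratified by sex and two prespecified age bands. Each assignment is made after the baseline ActiGraph has been returned and the BREQ-3 completed. It is released only once the participant's ID, sex and age band are locked. Recruiting staff see neither the list nor past assignments, and cannot alter an assignment.

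Minimisation on the same factors with a random element is an acceptable alternative.

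Also add sex to the baseline variables, and include sex and age (as a continuous variable) in every between-group ANCOVA whatever their observed correlations. Two age bands still leave sizeable differences in mean age in roughly a third of runs.

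If allocation has already taken place, state the method actually used and make the ANCOVA change.

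The cost is protocol wording and a short script, with no added participants or visits. The real drawback is some predictability if staff track assignments: about 45% correct guesses with mixed blocks, 49% with fixed blocks of 4 and 56–57% or slightly more with 80% minimisation. Concealing the list and past assignments is therefore part of the fix, and mixed blocks are the better first choice. They give up a little sex balance compared with fixed blocks of 4.

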Title: A Study to Test the Effectiveness of Different Interventions to Improve Physical Activity in Adults.

NCT Number: NCT04902014

Document Date: 9/8/2022

Background

Physical Activity (PA) and Health

According to the Centers for Disease Control and Prevention (CDC), adults (≥ 18 years) should participate in at least 150 minutes (two hours and thirty minutes) moderate-intensity physical activity (MPA) per week, or 75 to 150 minutes of vigorous intensity physical activity (VPA) per week, or some combination of both.¹ This level of PA is associated with substantial health benefits including improvements in cardiovascular health, muscular fitness, and cognitive function.¹ More than two thirds of U.S. adults do not meet these guidelines and have a 67% higher risk for all-cause mortality and contribute to the \$117 billion dollars in health care costs associated with physical inactivity.¹⁴

Self-Determination Theory and Physical Activity

Behavior-change theory-driven interventions and in particular those based in Self-Determination Theory (SDT) have been successful in improving PA participation in a variety of populations, in part due to a focus on intrinsic motivation.^{12,39-43} Behaviors that are intrinsically motivated are undertaken for the sake of the behavior itself; inherent satisfaction is the reward.¹⁰ In contrast, extrinsic motivation is associated with motivation by external factors and at its extreme, motivation by coercion.¹⁰ More autonomous, or intrinsic motivation, is correlated to long-term PA engagement while extrinsic motivation has been shown to be effective in PA initiation, but not sustainability.^{9,17}

Wearable Fitness Trackers to Improve Physical Activity Engagement

A promising tool to enhance PA participation is the use of a wearable fitness tracker (WFT) such as a Fitbit or Apple Watch. The small, relatively low-cost, and user friendly WFTs have been developed to support sedentary or under-active individuals in increasing their PA

engagement.¹⁸ Short term studies have indicated that WFT use increases both self-reported PA and objectively measured PA in adults.^{44,45} However, this improvement is not sustained in a majority of individuals.⁴⁶⁻⁵¹ Furthermore, it is known that most WFT consumers discontinue tracker use within six months of purchase.⁵² Therefore, it continues to be relatively unknown whether or not WFT impact motivation for PA or PA behavior in the long-term.⁵⁰

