MI: The individuals will be scheduled for and participate in six biweekly remote SDT based MI sessions. These sessions will take place via video calling platforms like Microsoft Teams, Zoom, or Skype. The MI sessions will be conducted by a PhD student who has been trained by a MI practitioner. Participants will be provided a log book and will be asked to log their PA, with the goal of completing at least 150 minutes of PA per week. These participants will also receive general physical activity guidelines education and information on strategies to reach the recommended amount of activity per week during the initial baseline assessment meeting. Participants in this condition will be asked to NOT wear a WFT of their own over the course of the intervention.

WFT+MI: These individuals will be given the wrist-worn WFT, be instructed to wear it for the duration of the study AND be scheduled for six SDT based remote MI sessions. These participants will also be trained by a member of our team on how to utilize the WFT and associated application. They will be instructed to try to complete 150 minutes of PA per week. Researchers will have the capability to track participant daily PA via the WFT and associated API. These participants will also receive general physical activity guidelines education and information on strategies to reach the recommended amount of activity per week during the initial baseline assessment meeting. Participants in this condition will be asked to ONLY wear the WFT provided to them by researchers.

PA Education Control: These participants will receive general physical activity guidelines education and information on strategies to reach the recommended amount of activity per week during the initial baseline assessment meeting. Participants will be asked to NOT wear a WFT of their own over the course of the intervention. At the conclusion of the study, these participants will be offered the chance to participate in one MI session.

Outcome measures: The following outcome measures will be collected at baseline, and at the completion of the twelve-week intervention.

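### The rule against own trackers in the MI and control arms covers only worn devices, so phone activity apps are a permitted and unrecorded source of part of the tracker's feedback

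*Combined protocol and SAP*

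**What the plan says.** Under Description of Intervention, the PA Education Control arm has this rule: "Participants will be asked to NOT wear a WFT of their own over the course of the intervention". The MI arm has the same rule: "Participants in this condition will be asked to NOT wear a WFT of their own over the course of the intervention". The two tracker arms are asked to wear only the device supplied by the study.

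The Background section treats the tracker as something worn, introducing it as "the use of a wearable fitness tracker (WFT) such as a Fitbit or Apple Watch". A phone app is not named there or in the restriction.

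The eligibility criteria under Participant Recruitment and Health Screening apply to all arms: "They must own an Android or iPhone smartphone device and be willing to download a mobile application onto that device".

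The WFT arm description lists the feedback supplied: "The intended WFT tracks daily steps, miles traveled, kcals expended, and daily activity time". It also makes the phone part of the intervention: "They will also be instructed to download the corresponding mobile application on their smartphones to be used for the duration of the study".

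No section restricts, asks about or records phone-based tracking in the MI or control arms. The nearest rule, in the eligibility criteria, concerns joining other organised activity programmes. Under Outcome measures, daily activity comes from the tracker app in the tracker arms and from self-report in the MI arm; no daily source is given for control. The Data Analysis section has no variable for tracking outside the assigned arm.

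**The concern.** The sponsor chose to bar participants' own trackers in the two non-tracker arms, evidently to keep a contrast between having and not having device feedback. The rule closes the worn-device route to that feedback and leaves the phone route open, and eligibility guarantees that every MI and control participant has a phone.

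At stake are the two contrasts that estimate what the tracker adds: WFT v control, and WFT+MI v MI. If non-tracker participants obtain some of the same feedback, both contrasts shrink. Because app use is not recorded, a null tracker result could not then be separated from a diluted one. The trial aims for 32 completers in four arms, which is 32/4 = 8 per arm if allocation is equal (the protocol does not state the ratio), so it has little room for such a loss.

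**Working it through.** **Inputs from the documents.** Four arms; 40 to be recruited and 32 to complete; a wear-only restriction in MI and control; smartphone ownership in all arms; an app as part of the tracker intervention. The protocol gives no effect size, standard deviation, power or within-person correlation, so the target of 32 cannot be rebuilt. The two totals imply 1 − 32/40 = 20% attrition, which shows only that they agree with each other.

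**Inputs that must be assumed.** That a phone app can give activity feedback without a worn device is general knowledge; the only app the protocol describes is the tracker's companion. Let q be the share of non-tracker participants using such an app, and f the fraction of the tracker effect it gives them. Neither has a source in the documents.

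**Dilution if apps add nothing for tracker wearers.** The share of the true contrast that remains is 1 − q·f:

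| q | f | q·f | Remaining contrast |
|---|---|---|---|
| 0.2 | 0.25 | 0.05 | 0.95 |
| 0.3 | 0.5 | 0.15 | 0.85 |
| 0.5 | 0.75 | 0.375 | 0.625 |

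**Allowing for app use in the tracker arms.** Let a share p of tracker participants also use a separate app that adds a fraction g of the tracker effect on top of the tracker. The remaining contrast becomes 1 + p·g − q·f. With p = q = 0.3 and g = f = 0.5 it is 1 + 0.15 − 0.15 = 1, so equal use with additive effects causes no dilution. With g = 0, where the app merely stands in for the tracker, it returns to 0.85. Dilution therefore requires that app use is greater in the non-tracker arms or that the app substitutes for the tracker.

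**Effect on power, for scale only.** Take an unadjusted comparison of 8 v 8 at two-sided 0.05 with an assumed starting power of 80%, which requires a difference of 1.51 SD. If 10%, 20% or 30% of the effect leaks, power falls to about 71%, 61% or 50%. The starting power and the leakage are both assumptions.

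**Which contrasts are exposed.**
- WFT v control and WFT+MI v MI: exposed, toward no difference.
- WFT+MI v WFT: not affected, since both arms have the tracker.
- MI v control: affected only if app use differs between those two arms.

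**The case against.** The strongest reply is that the protocol never states that its target is device feedback against none. All participants own smartphones, so existing phone tracking is a background common to every arm, and people were enrolled because they were not meeting the activity guideline with whatever apps they already had. What a tracker adds for ordinary smartphone owners is a legitimate question, and on that view only new uptake after randomisation, concentrated in the non-tracker arms, is contamination. This stands in part. It is a reason to separate prior use from new uptake, which the plan cannot do at present. It does not explain why the sponsor barred own trackers but left phone tracking unmentioned.

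A reader might infer that a compliant control participant gets most of what the tracker offers. The documents do not support that. The tracker arms also receive a wrist-worn device with its own screen, staff training and researcher access to daily activity, and the WFT arm submits goals every two weeks. An app found independently brings neither the training, the researcher access nor the goal submission.

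Two further inferences go beyond the text. The MI arm's log ("Participants will be provided a log book and will be asked to log their PA") is planned self-monitoring, and it is conjecture that it would send participants to a phone counter. What recruits are told about apps cannot be judged from an eligibility criterion when the consent pages are not available.

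Finally, naming phone trackers in an instruction could draw attention to them and make the comparator less like ordinary phone owners. That is a real cost, though a modest one.

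**Conclusion.** The gap is plain in the text: the rule against own trackers is limited to worn devices, every non-tracker participant has another possible route to part of the same feedback, and use of that route is not recorded. The consequence is a risk of dilution toward no difference in WFT v control and WFT+MI v MI, conditional on app use being greater in the non-tracker arms or replacing what the tracker supplies.

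The size is unknown. The range of 0.95 to 0.625 is set by the assumed q and f, so it estimates nothing about this trial. A reader might go further and conclude that the tracker comparisons are biased by a known amount, or are invalid. The documents support neither, since they contain no information on how often apps are used or what they achieve. The point merits a change because the repair is cheap and extends a safeguard the sponsor already chose.

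**What to change.** In the MI and PA Education Control descriptions, extend the existing instruction so that participants are asked neither to wear their own tracker nor to actively use a phone activity- or step-tracking app during the intervention.

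Alongside the online questionnaire, add one question on use of such apps, at baseline and at week 12, in all four arms. The baseline answer identifies prior use, the change identifies new uptake, and residual contamination can be reported by arm.

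The cost is one phrase in two arm descriptions and one questionnaire item. The instruction cannot be fully enforced (nor can the present one on worn trackers), and it places a small extra restriction on MI and control participants.

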- **Objectively measured PA engagement:** PA will be objectively measured by one week of actigraphy using the ActiGraph wGT3-BT activity monitor. Participants will be given the ActiGraph and will be instructed to wear it on a provided elastic belt on their non-dominant hip for one week. They will be given a log to record times that they removed the ActiGraph, which should only be when showering, bathing, or otherwise coming into contact with water. At the conclusion of the week, the ActiGraph data will be downloaded using ActivLife software. Daily PA will be assessed via the WFT

application for individuals in the WFT+MI and WFT groups, and via self-report for the MI group.

- **Motivation for PA:** Motivation for PA will be assessed using the Behavioral Regulation in Exercise Questionnaire (BREQ-3). This instrument is one of the most widely used in PA and exercise motivation research and has been validated in this population.^{21,22} This survey will be accessed via a secure online link.
- **Covariates:** Each of the following covariates will be collected pre-intervention: age, race/ethnicity, education level, family affluence, and height/weight (BMI). All, except height and weight will be collected with self-report. Height and weight will be measured by lab personnel during the first visit to the lab.

Data Analysis

Means and standard deviations of the following variables will be calculated: baseline and follow-up MVPA, steps, and energy expenditure, baseline and follow-up scores for PA motivation subscales, and participant age and BMI. Paired t-tests will be used to compare within subjects pre-participation values from post-participation values for PA, and motivation variables by group. ANCOVA will be used to compare between subjects differences in outcome variables by group. Models will be developed based on covariate correlation with outcome variables and other covariates.

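### Personal trackers are ruled out in MI and control only during the intervention, not in the baseline ActiGraph week, so the within-group pre-post tests are not like-for-like for current wearers

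*Combined protocol and SAP*

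**What the plan says.** The eligibility text (Methods, Participant Recruitment and Health Screening) treats trackers only as a matter of willingness: "They also must be willing to potentially wear a WFT and/or attend bi-weekly remote MI". It does not exclude people who already wear one, set a washout, or mention asking about current use. After consent, "Participants will wear the accelerometer for the subsequent 7 days to provide baseline data on their baseline level of PA". No rule on personal devices is given for that week. The arm is disclosed later, at the remote education session: "During this remote meeting, participants will be informed as to which group they have been randomized into".

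The device rules then differ by arm (Description of Intervention):

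- Control: "Participants will be asked to NOT wear a WFT of their own over the course of the intervention".
- MI: "Participants in this condition will be asked to NOT wear a WFT of their own over the course of the intervention".
- WFT and WFT+MI: "Participants in this condition will be asked to ONLY wear the WFT provided to them by researchers".

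Balancing is on age and sex ("To control for age and sex, participants will be age- and sex-matched in each group"). Tracker use is not among the covariates listed under Outcome measures. Data Analysis plans paired t-tests of pre against post values within each group, and ANCOVA between groups.

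**The concern.** The instruction to MI and control presupposes that some participants own a tracker. It is specific to the arm, and participants learn their arm only after the baseline week, so it cannot apply to that week. A current wearer in MI or control who complies goes from tracker on at baseline to tracker off afterwards. A current wearer in a WFT arm exchanges one device for another.

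The within-group tests are what is at stake. In MI and control, part of the measured change would be the loss of a device: any gain from MI would be understated, and control could appear to decline. In the WFT arms, the gain from being given a tracker would be diluted. Because the plan does not record current use, nobody could later say how large either effect was.

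**Working it through.** **Step 1. Device status at each measurement.**

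| Participant | Arm | Baseline week | Follow-up |
|---|---|---|---|
| Not a current wearer | MI, control | none | none |
| Not a current wearer | WFT, WFT+MI | none | study tracker |
| Current wearer | MI, control | own tracker | none, if compliant |
| Current wearer | WFT, WFT+MI | own tracker | study tracker |

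**Step 2. Inputs.** The plan gives no figure on this point to reproduce. Let p be the share wearing a tracker in the baseline week and D the activity a tracker adds, in SD units. Neither is in the documents; I assume p = 0.1 to 0.4 and D = 0.3 to 0.5. The plan aims for 32 completers, which is 32/4 = 8 per arm if allocation is equal (also assumed).

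**Step 3. Within-group change due to trackers.**

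- MI and control: (1-p) x 0 + p x (-D) = -pD. Smallest: 0.1 x 0.3 = 0.03. Largest: 0.4 x 0.5 = 0.20. The shift is -0.03 to -0.20 SD.
- WFT arms: (1-p) x D + p x 0 = (1-p)D. This is 1 - 0.4 = 60% to 1 - 0.1 = 90% of D.
- At p = 0 these are 0 and D, so there is no distortion.

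**Step 4. Between-arm contrast, starting and stopping equal and opposite.** (1-p)D - (-pD) = D for every p. At p = 0.4 and D = 0.5: 0.30 + 0.20 = 0.50, the full effect.

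**Step 5. Between-arm contrast, starting and stopping unequal.** Let starting add s and stopping cost w. The contrast is (1-p)s + pw. Assume s = 0.3 and w from 0 to 0.5:

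- p = 0.1: 0.27 + 0 = 0.27 to 0.27 + 0.05 = 0.32
- p = 0.4: 0.18 + 0 = 0.18 to 0.18 + 0.20 = 0.38

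At w = s = 0.3 it returns 0.30. The departure can go either way.

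**Step 6. Effect of an earlier ban.** If nobody wears a tracker at baseline, and the effect of stopping shows within that week, then in the model of Step 3 the MI and control change has no tracker component and the WFT-arm change is D. Follow-up status in the table is unchanged, so the contrast in Step 5 is unchanged too.

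**Step 7. Chance imbalance.** For two independent Binomial(8, p) counts, the probability that they differ by two or more is 34% at p = 0.2 and 41% at p = 0.3. Two extra wearers in an arm of 8 shift its mean change by 2/8 x 0.3 to 0.5 = 0.075 to 0.125 SD. The standard error of a difference between two arms of 8 is the square root of 2/8, or 0.5 SD.

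**The case against.** The strongest reply is that the randomised comparison survives. The baseline week is over before anyone knows their arm, so tracker wear in it cannot differ by arm in expectation, and Step 4 shows the two within-arm distortions offsetting exactly. This stands. A reader might infer that tracker withdrawal biases the WFT-versus-control ANCOVA; the documents do not support that. If starting and stopping differ in size, the contrast becomes a mixture of starting versus having none and continuing versus stopping. That mixture comes from enrolling wearers at all, its direction is not fixed, and moving the ban does not remove it. MI versus control is not differentially affected in expectation, since both arms have the same rule.

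A reader might also take the 34-41% chance of unequal numbers of wearers as a separate defect. It is ordinary sampling error: the resulting shift is small beside a standard error of 0.5 SD, and an earlier ban would not balance the arms.

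It is also fair to say that paired t-tests are not the randomised comparison and already absorb time effects and regression to the mean. But the plan specifies them for every group, and this distortion is avoidable.

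The assumed values may be high. The Background says that most buyers give up their tracker within half a year and that activity gains usually fade, and entrants must fall short of the activity guideline. Both suggest fewer active wearers and a smaller loss on stopping. That bears on size, not on the gap.

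Finally, the screening form is not shown and the consent pages were removed, so a question or instruction there cannot be ruled out.

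**Conclusion.** The point holds for the within-group paired t-tests. As the visible text stands, they compare tracker on with tracker off for compliant current wearers in MI and control, and tracker on with tracker on for wearers in the WFT arms. Under the assumed ranges the size is -0.03 to -0.20 SD in MI and control, and 60-90% of the true gain in the WFT arms. It is zero if no current wearer enrols.

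This rests on assumed values of p and D, on compliance (participants are asked, not compelled), and on the instruction still applying when follow-up activity is measured. The plan places follow-up at the end of the twelve weeks but does not say whether the follow-up ActiGraph week lies inside the ban. If wearers had resumed by then, the shift would be smaller.

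The point does not extend to a bias in the randomised ANCOVA. It is a modest flaw in a secondary reading of the data, worth correcting because the correction is cheap.

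**What to change.** At consent, ask all participants not to wear a personal tracker from the start of the baseline ActiGraph week. In MI and control, continue this explicitly through the follow-up ActiGraph week. Add one question on current tracker use to the screening form, report the answers by arm, and give a sensitivity ANCOVA that adjusts for current use. If few wearers enrol, the sponsor can then show it.

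Nobody is excluded and the sample size does not change. Wearers go about a week longer without their device, and their baseline becomes device-free rather than habitual activity, which should be stated because the plan wants that week to capture their baseline level. The self-reported measures, including the motivation questionnaire, are administered at the baseline session before the ActiGraph week, so the earlier instruction would not alter baseline motivation scores; for those, the recorded use is the only safeguard. The mixture in the between-arm contrast also remains, and the sensitivity analysis can only describe it.
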